4.1.2. Inpatient stay

Participants will be admitted to the study site on Day -1. They will remain inpatient until discharge on Day 7 after study procedures are complete.

Dosing

Dosing will occur on Day 1. Intended doses of LY3819253 are as follows:

- Cohort 1: 350 mg
- Cohort 2: 700 mg
- Cohort 3 (optional): 700 mg (alternative injection volumes)

See Section 6.1 for detail of injection volumes.

Participants will undergo PK sampling and safety assessment after dosing.

For Cohorts 1 and 2, a safety review will be conducted to determine whether it is appropriate to proceed with dosing of the next cohort. This safety review will be conducted based on data from at least 4 participants, after at least 4 days after dosing.

Sentinel dosing

Cohort 1 will include sentinel dosing. The first 2 participants will be randomized and dosed (1 LY3819253:1 placebo).

The investigator and the Lilly sponsor team are responsible for determining if safety and tolerability is acceptable to continue with dosing subsequent participants.

Tolerability as measured by ISRs and their severity is anticipated to be the main safety consideration for this assessment. While no serious systemic reactions have been seen with LY3819253 to date, participants will be closely monitored.

If the investigator and Lilly sponsor team determine that safety and tolerability is acceptable, the remaining participants in the cohort will be dosed on the next day.

Cohort 2 and the optional Cohort 3 will not include sentinel dosing.

Postdose sampling

On Days 1 through 7, participants will undergo PK sampling and safety assessment as shown in the SoA (Section 1.3).

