1.3. Schedule of Activities (SoA)

Procedure / Assessments	Screening	Treatment Period								Follow-up Visits				Comment
Visit Number	V1	V2								V3	V4	V5	V6/ ED	
Week(s)		0								2	4	8	12	
Study Day	-14 to -1	-1	1	2	3	4	5	6	7	15 ±2d	29 ±3d	60 ±3d	85 ±3d	
Informed consent (written)	X													
Review/confirm I/E criteria	X	X												After screening, ensure participants continue to meet I/E criteria.
Medical history including pre-existing conditions	X													
Weight/height	X												X	Height at screening only.
Urinalysis	X								X					
COVID-19 clinical screening	X	X								X	X	X	X	Symptoms and recent contact (see Section 5.2 for a description of symptoms and close contact). At designated timepoints and as needed during the study.
SARS-CoV-2 serology		X								X	X	X	X	Serology results are not needed before dosing.

Procedure / Assessments	Screening	Treatment Period								Follow-up Visits				Comment
	Visit Number	V1	V2								V3	V4	V5	
Week(s)		0								2	4	8	12	
Study Day	-14 to -1	-1	1	2	3	4	5	6	7	15 ±2d	29 ±3d	60 ±3d	85 ±3d	
SARS-CoV-2 point-of-care test	X	X												Additional point-of-care tests may be conducted at the investigator’s discretion. See Section 8.3.7.
Naso-pharyngeal swab			X											Can be before or after LY3819253 administration. For research purposes. See Section 8.3.7.
Nasal swab									X					For research purposes. This swab may be taken if a point-of-care test is done during the study, as described in Section 8.3.7.
Admission to study site		X												
Discharge from study site									X					
Physical examination Medical assessment	X	X	Pre-dose			X			X	As needed			X	Full PE/MA at screening and Visit 6/ED. Symptom-directed PE/MA at all other indicated time points and as deemed necessary by the investigator or designee.

Procedure / Assessments	Screening	Treatment Period								Follow-up Visits				Comment
Visit Number	V1	V2								V3	V4	V5	V6/ ED	
Week(s)		0								2	4	8	12	
Study Day	-14 to -1	-1	1	2	3	4	5	6	7	15 ±2d	29 ±3d	60 ±3d	85 ±3d	
Vital signs: blood pressure, body temperature, pulse rate ^a	X	X	Predose	24 h (±2 h)		X			X	X	X	X	X	Vital signs should be taken following at least 5-min rest in a supine position. Vital signs may be taken any time prior to dosing. If screening takes place on Day -1, there is no need to take vital signs twice on Day -1.
Single 12-lead ECG	X													
Concomitant medications review	X	X								X	X	X	X	

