AE review	X	X	Predose	X	X	X	X	X	X	X	X	X	X	AEs to be reviewed only after participant has signed the study ICF.
HIV, hepatitis B/C serology	X													

Procedure / Assessments	Screening	Treatment Period								Follow-up Visits				Comment
Visit Number	V1	V2								V3	V4	V5	V6/ED	
Week(s)		0								2	4	8	12	
Study Day	-14 to -1	-1	1	2	3	4	5	6	7	15 ±2d	29 ±3d	60 ±3d	85 ±3d	
Pregnancy test (women only) ^b	X	X											X	Serum pregnancy test at screening, urine test at other timepoints. Day -1 urine test refers to test at admission; this is not needed if admissions is on the same day as screening. Postdose urine test(s) can be performed at the judgment of the investigator, if pregnancy is suspected.
Clinical laboratory tests ^a	X	X							X	X	X	X	X	Fasting is not required for these tests. If screening takes place on Day -1, there is no need to conduct these tests twice on Day -1.
Breath or urine ethanol screen		X												Ethanol screen may be repeated at other time points at the discretion of the investigator.
Urine drug screen	X	X												Day -1 urine test refers to test at admission; this is not needed if admission occurs on the same day as screening. Drug screen may be repeated at other time points at the discretion of the investigator.

Procedure / Assessments	Screening	Treatment Period								Follow-up Visits				Comment
	Visit Number	V1	V2								V3	V4	V5	
Week(s)		0								2	4	8	12	
Study Day	-14 to -1	-1	1	2	3	4	5	6	7	15 ±2d	29 ±3d	60 ±3d	85 ±3d	
SC LY3819253 or placebo dosing			X											
LY3819253 PK sampling ^a			X	X	X	X	X	X	X	X	X	X	X	Day 1 collection should be taken up to 4h postdose ±4h. The exact time of draw must be recorded. For Day 2 onwards, PK samples may be taken at any time after vital signs.
Injection site assessments			Predose; 1min ±1min, 10min ±2min, 30min ±5min, 240min ± 10min	24h ±4h	X	X	X	X	X	X	X	X	X	Timepoints include ISR assessment, VAS, if pain is reported, and the exploratory Scarletred tool. Scarletred timing is flexible and not confined to the windows shown, except for predose. See Section 8.2.5 for detail.
Immunogenicity			Predose							X	X	X	X	
Serum sample for exploratory biomarkers ^a			Predose		X					X	X	X	X	
Pharmacogenetics sample ^a			Predose											For storage only.

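### Day 1 schedules four post-dose injection-site checks but no post-dose vital signs, and the sentinel step does not require any before release: a minor, cheap improvement

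*Protocol*

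**What the plan says.** Protocol 8.2 places the planned time points for all safety assessments in the SoA (Protocol 1.3). On Day 1 the SoA gives the injection site a predose check and then "1min ±1min, 10min ±2min, 30min ±5min, 240min ± 10min". In the same column, vital signs, AE review and physical examination/medical assessment are marked predose only. After dosing, vital signs next appear at 24 h ±2 h, AE review on Day 2 without a clock time, and the medical assessment on Day 4.

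Protocol 4.1.2 gives Cohort 1 a sentinel step: "The first 2 participants will be randomized and dosed (1 LY3819253:1 placebo"). On what the decision rests on, it says: "Tolerability as measured by ISRs and their severity is anticipated to be the main safety consideration for this assessment". It adds: "While no serious systemic reactions have been seen with LY3819253 to date, participants will be closely monitored". Release is conditional on a joint judgement of investigator and sponsor: "Lilly sponsor team determine that safety and tolerability is acceptable, the remaining participants in the cohort will be dosed on the next day". SAP 5.3 repeats this text. Neither document names a vital-sign reading, a data set or a minimum observation time for the decision.

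Vital signs are a named secondary endpoint (Protocol 3). Protocol 4.2 describes the study as the first to give this new formulation by the SC route in humans.

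**The concern.** The first hours after a first SC dose are watched closely at the injection site, while nothing systemic is on the schedule. The programme before this study was intravenous (IV). Protocol 2.2.1.1 reports 4 infusion reactions in Study PYAB, where 88 participants had received drug or placebo. They began within about 30 minutes of the start of infusion and were considered related to treatment. Those data are blinded and IV, so the rate cannot be carried over to SC dosing. They do show that early systemic observation is relevant to this antibody.

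Two things are at stake. A secondary endpoint has no planned value between predose and 22 h, for drug or placebo. And the decision to dose the rest of Cohort 1 can be taken without a single scheduled post-dose vital-sign reading from the sentinels.

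**Working it through.** No sample-size, power or alpha figure bears on this point. The check is a reading of the SoA cells and the timing that follows from them. Each relevant row has 13 cells, matching the 13 day columns (Screening, -1, 1 to 7, 15, 29, 60, 85).

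| Assessment | Day 1 | Next scheduled after Day 1 | Day 1 post-dose count |
|---|---|---|---|
| Injection site | Predose; 1, 10, 30, 240 min | 24 h ±4 h | 4 |
| Vital signs | Predose | 24 h ±2 h | 0 |
| AE review | Predose | Day 2, untimed | 0 |
| Physical examination/medical assessment | Predose | Day 4 | 0 |

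**Timing**
- Post-dose vital signs are planned on Days 2, 4, 7, 15, 29, 60 and 85: 7 time points. The earliest is 24 - 2 = 22 h and the latest for that first set is 24 + 2 = 26 h, so 0 of 7 fall before 22 h.
- The last Day 1 injection-site check falls between 240 - 10 = 230 min and 240 + 10 = 250 min.
- The gap from that check to the first post-dose vital signs is 22 - 250/60 = 17.8 h at the shortest and 26 - 230/60 = 22.2 h at the longest.

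**The sentinel step**
- Cohort 1 has at least 9 participants (7 active, 2 placebo). Less the 2 sentinels (1 and 1), the decision releases at least 7 (6 active, 1 placebo).
- The only timing given is the next day. If dosing starts 22 h or less after the sentinels' dose, their first post-dose set is not yet due. From 22 to 26 h it may or may not have been taken. The documents give no clock times, so whether release would in fact come first is unknown. They permit it.
- The protocol does define inputs at the next level: the cohort review in 6.6.1 needs at least 4 active participants through Day 4. The sentinel step has no counterpart.

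**With the suggested set**
- At the 240-min contact, the first planned post-dose reading moves from 22 to 26 h down to 230 to 250 min (3.8 to 4.2 h). An optional 30-min set would bring it to 25 to 35 min.
- Burden at the maximum of 36 participants: 1 x 36 = 36 sets, or 2 x 36 = 72 with the 30-min set. The SoA requires 5 min supine rest for each.

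**The case against.** The strongest reply is that the protocol already covers what matters. Participants are inpatients to Day 7, and Protocol 2.3 says this allows close monitoring for hypersensitivity and injection-site reactions. AEs are collected continuously (8.3.1), staff see each participant at four timed contacts on Day 1, and extra vital signs (8.2.2) or a medical assessment (SoA comment) can be done whenever the investigator sees a need. Protocol 4.2 states that the 4-day review with inpatient status is sufficient to detect an acute systemic response that would preclude escalation. Protocol 4.3 expects 350 mg SC to give lower peak and total exposure than the IV doses already tested. All of this stands. Discretionary readings, however, are not guaranteed and need not be taken at matching times in the two arms, and the statement in 4.2 concerns escalation, not sentinel release.

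Three stronger readings are tempting, and the documents do not support them:
- *That participants go unmonitored on Day 1.* They do not. The gap is in scheduled measurement. Because AE capture is already continuous, a Day 1 AE entry would add a prompt and no new data stream.
- *That systemic findings are excluded from the sentinel decision.* The judgement covers safety and tolerability, and injection-site reactions are only the anticipated main consideration.
- *That unmeasured changes disable the stopping rules in 6.6.3 at the sentinel step.* The first rule needs 3 or more participants with related AEs, and there are 2 sentinels. The second needs a serious or severe related AE, and 10.3.3 defines severe by symptoms that prevent usual activities. A transient asymptomatic change would not qualify unless judged serious.

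It is also fair to say that, with one active sentinel, an added reading detects little at that step. Its larger value is a timed Day 1 record for everyone, including Cohort 2, which goes to 700 mg without sentinels.

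**Conclusion.** The point holds as a minor, low-cost improvement. As scheduled, transient and asymptomatic changes in blood pressure, pulse or temperature in the first 22 h have no planned measurement in either arm, and release of the rest of Cohort 1 can precede the first scheduled post-dose vital signs.

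The size is 0 of 7 planned post-dose vital-sign time points before 22 h, against 4 timed injection-site checks on Day 1, with at least 7 participants released on the sentinel decision. The documents give no rate for such changes after SC dosing, and none is claimed. The escalation review is unaffected: by Day 4 the Day 2 and Day 4 vital signs are on the schedule.

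The conclusion rests on the SoA being the complete list of planned safety time points, as 8.2 says, and on next-day dosing carrying no minimum interval.

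**What to change.** 1. **SoA.** In all cohorts, add one Day 1 post-dose vital-signs set, with an AE prompt, at the existing 240-min contact. A second set at 30 min is optional. For the Day 1 pharmacokinetic sample the SoA says: "Day 1 collection should be taken up to 4h postdose ±4h". The draw may therefore fall at the same contact; if it does, take vital signs first, as SoA footnote a already requires.
2. **Protocol 4.1.2.** State that the sentinels' Day 1 post-dose vital signs and AEs to date are reviewed before the remaining participants are dosed. Align the descriptive text in SAP 5.3.
3. **SAP 9.4.4.** No change is needed. It summarises vital signs data by treatment without listing time points, and the Day 1 predose baseline stays as it is.

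The cost is at most 36 extra sets (72 with the 30-min set), each with 5 min supine rest, at contacts that already exist. The 30-min contact is the busier one, because reactions are assessed for each of 2 or 3 injections, so 240 min is the better single choice. Next-day dosing is not delayed, because the reading is available the same day.

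Requiring the sentinels' 24 h set as well is optional. If next-day dosing would otherwise start at the sentinels' clock time, a reading at 26 h would delay it by 26 - 24 = 2 h plus review time.

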4.1.3. Outpatient follow-up

Follow-up visits will be conducted through Day 85, as shown in the SoA (Section 1.3).

In the event a participant has suspected or confirmed SARS-CoV-2 infection, follow-up visits may be conducted at the participant's home.

4.2. Scientific Rationale for Study Design

This is the first study to evaluate a new formulation via SC route of administration in humans. This study will be conducted with healthy participants, rather than patients with COVID-19, because the important biopharmaceutic questions related to the new SC route of administration, such as PK and tolerability, will be more efficiently investigated in the healthy human population.

The 4-day safety review together with in-patient status after dosing is sufficient to detect an acute adverse systemic response that would preclude dose escalation.

Placebo will be used as a comparator to allow interpretation of safety and tolerability data following administration of LY3819253.

4.3. Justification for Dose

Previous studies have evaluated LY3819253 IV doses in a range of 700 mg to 7000 mg and shown to be safe and well tolerated.

For Study PYAG, the planned doses of LY3819253 350 mg and 700 mg have been chosen to evaluate PK following this new SC route of administration.

The calculated human AUC(0-∞) following a single IV dose at 700 mg was 54000 hr*µg/mL which is 14-fold lower than the AUC at the no-observed-adverse-effect level in the 21-day rat IV toxicology study [AUC(0-168hr) in rats at 500 mg/kg = 755000 hr*µg/mL].

The starting dose of 350 mg dose is expected to result in lower plasma concentrations (maximum drug concentration [C_{max}] and area under the concentration versus time curve [AUC]) tested with IV dosing in previous studies with LY3819253. The concentrations following 350-mg and 700-mg SC dosing are expected to be quantifiable for pharmacokinetic evaluation, including a model-based estimate of bioavailability.

4.4. End of Study Definition

A participant is considered to have completed the study if he/she has completed all required phases of the study including the last scheduled procedure shown in the SoA.

The end of the study is defined as the date of last scheduled procedure shown in the SoA for the last participant.

5. Study Population

Prospective approval of protocol deviations to recruitment and enrollment criteria, also known as protocol waivers or exemptions, *is not permitted*.

5.1. Inclusion Criteria

Participants are eligible to be included in the study only if all of the following criteria apply:

Age

1. are aged 18 to 60 years at the time of signing the informed consent.

Type of Participant and Disease Characteristics

2. are overtly healthy as determined by medical evaluation including medical history and physical examination
3. have safety laboratory test results within the reference range for the population at the study site, or results with acceptable deviations that are judged to be not clinically significant by the investigator
4. have venous access sufficient to allow for blood sampling as described in this protocol (SoA, Section 1.3)
5. are reliable and willing to make themselves available for the duration of the study
6. are willing to follow study procedures, including having nasal or nasopharyngeal swabs collected as described in this protocol (SoA, Section 1.3).

Weight

7. have a BMI within the range ≥ 18.5 to < 35 kg/m².

Sex

8. are male or female
 - a. male participants must agree to adhere to contraception restrictions
 - b. female participants must be of non-childbearing potential

Contraception requirements and definition of non-childbearing potential are detailed in Appendix 4 (Section 10.4).

Informed Consent

9. are capable of giving signed informed consent as described in Appendix 1 (Section 10.1), which includes compliance with the requirements and restrictions listed in the ICF and in this protocol

5.2. Exclusion Criteria

Participants are excluded from the study if any of the following criteria apply:

Medical Conditions

10. have current SARS-CoV-2 infection confirmed by nasal or nasal pharyngeal swab results at screening or Day -1.

11. have had prior SARS-CoV-2 infection within 6 weeks before screening, confirmed by either previous nucleic acid-based test, or previous serology
12. have suspected current SARS-CoV-2 infection, in the opinion of the investigator, based on either or both of the following:
 - a. a recent exposure to SARS-CoV-2, defined as:
 - living in the same household as a person with SARS-CoV-2;
 - having had direct physical contact with a person with SARS-CoV-2 (for example, shaking hands);
 - having unprotected direct contact with infectious secretions of a person with SARS-CoV-2 (for example, being coughed on or touching used paper tissues with a bare hand);
 - having had face-to-face contact with a person with SARS-CoV-2, within 2 meters and for more than 15 minutes
 - b. signs or symptoms that, in the opinion of the investigator, are suggestive of infection (for example, fever, dry cough, shortness of breath, hypoxia, etc.)
13. have a history or presence of cardiovascular (including hypertension), respiratory, hepatic, renal, gastrointestinal, endocrine, hematological, psychiatric, or neurological disorders that, in the opinion of the investigator, are capable of
 - a. significantly altering the absorption, metabolism, or elimination of drugs
 - b. constituting a risk while taking the investigational product, or
 - c. interfering with the interpretation of data
14. have clinically significant abnormal ECG results constituting a risk while taking the investigational product, as determined by the investigator
15. have an abnormal blood pressure as determined by the investigator. In case blood pressure appears to be abnormally high during the screening period, it is possible to repeat the measure(s) 1 time in a quiet room to avoid an exclusion due to the white coat effect
16. have significant allergies to humanized mAbs
17. have any of the following that are clinically significant:
 - a. multiple or severe drug allergies
 - b. intolerance to topical corticosteroids, or
 - c. severe posttreatment hypersensitivity reactions (including, but not limited to, erythema multiforme major, linear immunoglobulin A dermatosis, toxic epidermal necrolysis, or exfoliative dermatitis)
18. have known allergies to LY3819253, related compounds, or any components of the formulation
19. have had lymphoma, leukemia, or any malignancy within the past 5 years, except for basal cell or squamous epithelial carcinomas of the skin that have been resected with no evidence of metastatic disease for 3 years
20. have had breast cancer within the past 10 years
21. show evidence of HIV infection and/or positive human HIV antibodies
22. show evidence of current hepatitis C (that is, test positive for anti-hepatitis C antibody with confirmed presence of HCV RNA)

Note: Patients with a previous diagnosis of hepatitis C who received antiviral therapy and achieved a sustained virological response may be eligible for inclusion in the study, provided that they have no detectable HCV RNA on the screening HCV polymerase chain reaction test for this protocol. A sustained virological response is defined as an undetectable HCV RNA level 24 weeks after completion of a full, documented course of an approved antiviral therapy for HCV.

Patients who have spontaneously cleared HCV infection, defined as (1) a positive HCV antibody test and (2) a negative HCV RNA test, with no history of HCV antibody (anti-HCV) treatment, may be eligible for inclusion in the study, provided that they have no detectable HCV RNA at screening for this study.

23. have history of hepatitis B infection, or show evidence of current hepatitis B:
 - a. test positive for hepatitis B surface antigen, and/or
 - b. test positive for hepatitis B core antibody and negative for hepatitis B surface antibody

Prior/Concomitant Therapy

24. have received treatment with biologic agents (such as mAbs, including marketed drugs) within 3 months or 5 half-lives (whichever is longer) prior to dosing
25. have previously completed or withdrawn from this study and have previously received the investigational product
26. intend to use over-the-counter medication in the 7 days prior to dose administration or prescription medication in the 14 days prior to dose administration, with the exception of hormone replacement therapy, thyroid replacement medications, vitamin and mineral supplements and occasional use of acetaminophen. Note that acetaminophen is NOT allowed within 24 hours before dosing.

Prior/Concurrent Clinical Study Experience

27. are currently enrolled in a clinical study involving an investigational product or any other type of medical research judged not to be scientifically or medically compatible with this study
28. have participated in a clinical study involving an investigational product, with last dose within the past 30 days or 5 half-lives, whichever is longer, prior to dosing

Other Exclusions

29. are pregnant or breast feeding
30. have donated blood of more than 500 mL within the previous 3 months of study screening, or intend to donate blood during the course of the study
31. have an average weekly alcohol intake that exceeds 21 units per week (males) or 14 units per week (females), or are unwilling to stop alcohol consumption from 48 hours prior to admission to and while resident at the CRU (1 unit = 12 oz or 360 mL of beer; 5 oz or 150 mL of wine; 1.5 oz or 45 mL of distilled spirits)
32. currently smoke in excess of 10 cigarettes per day or are unwilling to abide by CRU smoking restrictions

33. regularly use known drugs of abuse and/or show positive findings on drug screening unless they were prescribed by a physician (for example, benzodiazepines).
34. are Lilly employees or are employees of a third-party organization involved with the study that requires exclusion of its employees or study site personnel directly affiliated with this study or their immediate families. Immediate family is defined as a spouse, biological or legal guardian, child, or sibling.
35. have tattoos or scars over the abdomen, or other factors (for example, rash or excessive folds of skin) that, in the investigator's opinion, would interfere with injection site assessments
36. in the opinion of the investigator or sponsor, are unsuitable for inclusion in the study

